4. MDS-UPDRS
5. NMSS
6. PDQ-39
7. EQ-5D
8. MoCA
9. BDI
10. MADRS
11. Timed motor tests as ON state only (for subjects on dopamine therapy)
12. Pharmacokinetics

C. Secondary Endpoints (Safety)

1. Routine assessments of AEs and SAEs
2. Dose limiting toxicities
3. Routine serum chemistries with liver function tests
4. C-SSRS
5. Routine hematology tests with coagulation tests
6. Electrocardiogram

D. Screening and Baseline Evaluation

D1. Physical Examination, height and weight

Complete physical exams will be conducted (excluding genital/rectal exam) at protocol specified study visits. The physical examination will consist of an examination of the following: general appearance, skin, head, eyes, ears, nose, throat, neck (including thyroid), lymph nodes, chest, heart, abdomen, and extremities.

Vital sign measurements (pulse rate, blood pressure and respiration rate) will be obtained in the sitting position (after the subject has been sitting for five minutes).

The findings from breast exam will be captured as part of the screening physical exam. The findings from breast exams conducted within 6 months of the screening visit and those collected as part of medical history, may be used for the screening physical exam.

Medical history and demographics including age, gender, race, will be collected at screening visit. Weight (kg) will be measured in ordinary indoor clothing (i.e., street clothes, scrubs, etc.) with shoes off. Height will be recorded in centimeters (cm) and need not be repeated after screening visit.

If clinically significant findings, as determined by the Investigator, are recorded for a particular symptom, sign or abnormal measurement, that measurement will be repeated at medically appropriate intervals until the value returns to an acceptable range, a specific diagnosis is established, or the condition is otherwise explained.

D2. Laboratory Evaluations

Subjects will have less than 100 mL of blood drawn over the course of the study.

The following variables will be collected at various times (as detailed in Section I).

- a. Hematology
 - a. Erythrocytes: red blood cell (RBC) count, hematocrit, hemoglobin, mean corpuscular volume (MCV)
 - b. Leukocytes: white blood cell count (WBC) and differential (basophils, eosinophils, lymphocytes, monocytes, and neutrophils). The differential can be recorded as an absolute value or percentages.
 - c. Platelets: platelet count
 - d. Coagulation: prothrombin time (PT) with INR, and partial thromboplastin time (PTT)
- b. Serum chemistry
 - a. Liver: Alkaline Phosphatase (ALP), ALT (serum glutamic-pyruvic transaminase [SGPT]), AST (serum glutamic-oxaloacetic transaminase [SGOT]), bilirubin (total and direct), gamma-glutamyl transferase (GGT), and lactic dehydrogenase (LDH)
 - b. Renal: blood urea nitrogen (BUN), and creatinine
 - c. Electrolytes: sodium, potassium, chloride and bicarbonate
 - d. General: creatine phosphokinase (CPK), total protein, albumin, calcium, magnesium, glucose, phosphate
 - e. Lipids: cholesterol (total), high-density lipoprotein (HDL) cholesterol, low-density lipoprotein (LDL), cholesterol, and triglycerides

- c. Urine pregnancy test
 - 1. Human chorionic gonadotropin (HCG) beta subunit will be measured on all female subjects of childbearing potential.

Laboratory tests that result in significantly abnormal values should be repeated for verification. Additional tests and other evaluations required to establish the significance or etiology of an abnormal result, or to monitor the course of an AE, should be obtained when clinically indicated. In particular, if a clinically significant abnormal result is observed that is not resolved by the final study visit, repeat tests should be performed to document resolution or stability of the abnormality.

Diagnoses associated with any NIH Common Terminology Criteria for Adverse Events (CTC v4.03) Grade 3 or 4 laboratory abnormalities will be recorded as adverse events (AEs) on the CRF. The recorded event should indicate the underlying abnormality or diagnosis (e.g., renal insufficiency) if known, as opposed to the observed deviation in laboratory results (e.g., elevated creatinine). Any additional relevant laboratory results obtained by the Investigator during the study will be supplied to the Sponsor.

D3. Dose Limiting Toxicity (DLT)

There were no DLTs noted in the phase 1 study; the dose-limiting (NOAEL) in nonclinical studies, as described in the protocol were increased LFTs (ALT, AST), rhabdomyolysis (elevated CPK), renal dysfunction (likely secondary to rhabdo), and marrow toxicity (most notably hemolysis). Therefore for this study, any increased LFT, BUN/Cr or CPK (or CK) should be considered related to study drug and should be designated as a DLT. If there is a DLT, a dose reduction will be attempted. Contact the medical monitor for further instructions.

D4. Columbia Suicide Severity Rating Scale (C-SSRS)

The C-SSRS is a semi-structured tool for assessing suicidal ideation (Questions 1-5) and behavior (Questions 6-10) through a series of questions.

E. Sample Collection Procedures, Bioanalytical Methods and Sample Shipment

Subject samples will be identified by unique sample codes.

Blood, urine, and cerebral spinal fluid samples will be collected for determination of levels of GSH cycle markers. Additional information about the collection, handling, storage, and shipment of the GSH cycle marker samples will be provided separately prior to start of the study.

F. Efficacy Evaluations

F1. Fasting Glutathione Cycle Biomarkers

Blood, urine, and CNS levels of oxidized and reduced GSH as well as GSH metabolites will be used to evaluate EPI-589 target engagement and ability to correct a key biochemical aspect of disease pathology.

F2. Study Clinical Assessments

The investigator or sub-investigator should be the primary administrator of these assessments, though they may delegate this study procedure to another qualified staff member on their team. It is recommended that the same administrator conduct this assessment on the same patient(s) throughout the study to ensure consistency when at all possible.

a. Parkinson's Disease Rating (MDS-UPDRS)

The MDS-UPDRS is a tool for monitoring the impact of PD, the degree of disability caused, and complications from treatment. Part I evaluates nonmotor experiences of daily living; Part II evaluates motor experiences of daily living; Part III is a motor examination and includes the Hoehn and Yahr scale; Part IV examines motor complications (e.g., motor fluctuations and dyskinesias).

Several questions from Part I and all questions from Part II are designed to be amenable to a patient/caregiver questionnaire format; the remaining interview (Part I and Part III) and examination (Part IV) are designed with the expectation they can be completed within 30 minutes. Each item is measured on a five-point scale.

b. Non-motor Symptoms (NMSS)

Non-motor symptoms are evaluated using the NMSS which is divided into 30 questions in 9 different domains including such symptoms as dribbling saliva, constipation, depression, sleep disorders, apathy, hallucinations and dementia. Symptoms are quantified based on their severity (using a scale of 0 to 3) and frequency (using a scale of 0 to 4). The final cumulative scores are derived from adding up the product of the frequency score times severity score for each of the 30 questions.

c. Parkinson's Disease Questionnaire (PDQ-39)

PDQ-39 is a self-administered questionnaire for patients with PD that has 39 questions relating to eight key areas of health and daily activities, including both motor and non-motor symptoms. It is scored on a scale of 0 to 100, with lower scores indicating better health, and high scores more severe symptoms.

d. EQ-5D

EQ-5D is a questionnaire designed to provide measures of health-related quality of life states, consisting in five domains (mobility, self-care, usual activities, pain/discomfort and anxiety/depression).

e. Montreal Cognitive Assessment (MoCA)

MoCA is a 30-point questionnaire for cognitive dysfunction. It assesses different cognitive domains: attention and concentration, executive functions, memory, language, visuo-constructional skills, conceptual thinking, calculations, and orientation. Severity ranges are approximately: 26 to 30 normal; 18 to 26 mild cognitive impairment; 10-17 moderate cognitive impairment; < 10 severe cognitive impairment.

f. Beck Depression Inventory (BDI)

The BDI is a self-reporting inventory that measures characteristic attitudes and symptoms of depression, including physical symptoms. Twenty-one questions have four responses each (rated 0 to 3) with a total cumulative score scale ranging from 1-10 considered normal) > 40 (extreme depression).

g. Montgomery and Asberg Depression rating scale (MADRS)

The MADRS is a clinician-rated tool for measuring changes in depressive symptom severity. Ten core symptoms and cognitive features are rated on a severity scale of 0 to 6. Higher scores indicate increasing depressive symptoms.

h. Timed motor tests as ON state only (for subjects on dopamine therapy)

Timed motor tests are simple, objective, quantitative measures for the assessment of Parkinson's disease. They include, in an on-medication and an off-medication state, timed recorded physical movements. Since missing dopamine could impair a subject's mobility including their ability to drive the next morning for study visits, the subjects should be encouraged to continue to take their dopamine as prescribed. In order to avoid missing PM dose of the dopamine the previous night, the sites can perform the TUG test on subjects as ON state only.

Space intentionally left blank

VIII. STATISTICAL CONSIDERATIONS

A. Statistical Analysis

In this subject-controlled, open label study the incidence of drug related SAEs in addition to changes from baseline to Month 3 for disease-relevant peripheral and CNS biomarkers as well as clinical measures will be calculated for each subject.

A1. Analysis Populations

Demographic characteristics and baseline efficacy data will be presented and summarized by treatment group for all subjects in the efficacy intent to treat (EITT) population. Demographic information will also be summarized by treatment group for the Safety population. No formal statistical comparisons will be made for either the EITT or Safety populations.

B. Efficacy Analysis

B1. Efficacy Variables

The efficacy variables in this study are:

1. Fasting blood-based glutathione cycle biomarkers
2. Fasting CNS biomarkers
3. Fasting urine-based biomarkers

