EPI-589 is an orally available compound that has been demonstrated in vitro and in vivo to cross the blood-brain-barrier. In 28-day, 91-day, 6-month, and 9-month repeat-dose toxicity studies in rat and cynomolgus monkey, the no observed adverse effect level (NOAEL) was 300 mg/kg/day, corresponding to terminal combined mean C_{max} values of 37,717 to 56,500 ng/mL (rat) and 14,300 to 24,500 ng/mL (monkey), and terminal combined mean area under the plasma concentration-time curve (AUC) values of 149,495 to 297,000 ng.h/mL (rat) and 47,300 to 124,000 ng.h/mL (monkey) (Studies 1660-038, 1660-039, 1660-063, 1660-064, 1660-079, and 1660-080).

The dose-limiting drug-associated toxicity observed in the 28-day, 3-month, and 9-month (monkey) animal studies was hemolysis in rat and significant acute toxicity leading to moribundity with indication of skeletal, renal, liver, and lymphoid tissue effects in monkey. All clinical program investigators have been required to monitor hematology parameters and clinical chemistry parameters for kidney, liver, and muscle function in all EPI-589 subjects. To date, no dose-limiting toxicities have been reported with EPI-589 in humans.

A phase 1 clinical study demonstrated that healthy young and elderly subjects administered 500 mg EPI-589 BID for 14 days showed mean C_{max} values of 1,890 to 1,960 ng/mL and mean AUC values of 10,480 to 11,000 ng.h/mL (Study EPI589-14-01). These plasma concentrations are well below the 300 mg/kg/day NOAEL exposure values in monkey, the most sensitive toxicity species, corresponding to repeat-dose exposure safety margins of approximately 7- to 12- fold for the mean C_{max} and 4- to 8-fold for the mean AUC.

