8. Age 40 to 75 years
9. Within 5 years of diagnosis of Parkinson's disease

For Genetic Subtype Subjects

10. A confirmed diagnosis of PD plus a genetic diagnosis consistent with PD, specifically PINK1, parkin, LRKK2 or other mitochondrial genetic subtype
11. Age 21 to 75 years

D2. Exclusion Criteria

1. Allergy to EPI-589 or other components of the EPI-589 tablet formulation
2. Use of antioxidant supplements, specifically vitamins E and C beyond the recommended daily allowance
3. Other Parkinsonian disorders
4. MoCA score of <24
5. Revised Hamilton Rating Scale for Depression ≥ 11
6. Parkinsonism due to drugs or toxins
7. Diagnosis of any other clinically significant neurologic disease that will confound the assessment of effect of study drug on disease progression
8. Malignancy within past two years
9. Pregnant or plans to become pregnant or breast feeding

10. History of stroke
11. History of brain surgery
12. Hepatic insufficiency with liver function tests (LFTs) > 3 times upper limit of normal
13. Renal insufficiency as defined by creatinine > 1.5 times normal
14. End stage cardiac failure
15. Participation within past 3 months and for duration of study in a trial of a device, drug or other therapy for PD

Space intentionally left blank

VI. STUDY PROCEDURES

A. Screening Visit

Screening evaluations will be performed within two months of first dose. The Investigator will inform each prospective subject of the nature of the study, explain the potential risks, and must obtain written informed consent from the subject prior to performing any study-related procedures and prior to the administration of study drug. Screening evaluations consist of the following:

1. Assessment of eligibility
2. Medical history, chart review
3. Receipt and review of previous testing including genetic tests
4. Physical examination* including vital signs
5. Height** and weight
6. 12-lead ECG
7. Laboratory assessments for hematology, coagulation, and serum chemistry*** (See Sections [VII.D2.a](#) and [VII.D2.b](#))
8. Urine pregnancy test (women of childbearing potential must have a negative urine pregnancy test; see Section [VII.D2.c](#))

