2. Added the term morning and evening dose to BID	To provide further clarification that dosing is twice daily rather than every 12 hours.
3. Non-clinical studies language	To provide updated information on nonclinical studies.
4. Changed the language under pharmacokinetics (PK) section	To clearly define the expected number of PK blood draws
5. Changed the timed motor test as ON state only (for subjects on dopamine therapy)	To clarify that sites can perform TUG test on subjects in ON state only
6. Dose Limiting Toxicity	To provide clear definition for dose limiting toxicities (DLTs)
7. Administration of clinical assessment	To clarify the primary administrator of the PD assessments for the study
8. Washout period for subjects on high doses of Vitamin E or C	To clarify the need for a 2 week wash out prior to enrollment for subjects on higher doses of vitamin C and E supplements
9. CBC differential as absolute or percentages	For better clarity about recording the values
10. CO ₂ for serum chemistry	CO ₂ is taken and assessed as bicarbonate in most clinical labs. Hence replaced the term Co2 as bicarbonate in the protocol. This is a venous sample.
11. Day 1 first dose language	To clarify that first dose may be taken same day as baseline visit after completing all assessments
12. Changed the height measurement to screening visit only	To clarify that height measurement need not be repeated after screening visit
13. Included breast exam as part of screening physical exam	To capture the findings from breast exam as part of the screening physical exam
14. Removed language in adverse event reporting	To clarify reporting for adverse events
15. Changed the AE language under post-treatment follow up	To clearly define the post treatment follow-up to be at least 10 days after last dose and if there are any ongoing or new AEs noted at month 3, then the follow up will be up to 30 days after last dose

DESCRIPTION OF CHANGES TO THE PROTOCOL

Changes to the protocol by section appear in the table below. Administrative and editorial clarifications, corrections or adjustments may not be individually identified.

In this summary document, ***bold italic*** font indicates additions to existing text, and ~~strikethrough~~ font indicates deleted text. The actual amended protocol does not include bold or strikethrough font to indicate changes.

Protocol Section	Modification

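### The DLT rule in VII.D3 has no grade and no explicit baseline reference, and it states no hemoglobin criterion although its own premise names hemolysis as dose-limiting

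*Protocol*

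**What the plan says.** Amendment 5.0 added section VII.D3. The Summary of Changes (item 6) gives its purpose: "To provide clear definition for dose limiting toxicities (DLTs".

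D3 has three steps.

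- **Premise.** The nonclinical dose-limiting findings were "increased LFTs (ALT, AST), rhabdomyolysis (elevated CPK), renal dysfunction (likely secondary to rhabdo), and marrow toxicity (most notably hemolysis".
- **Rule, introduced as following from the premise.** "any increased LFT, BUN/Cr or CPK (or CK) should be considered related to study drug and should be designated as a DLT".
- **Action.** "If there is a DLT, a dose reduction will be attempted. Contact the medical monitor for further instructions".

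These other sections bear on it:

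- VII.C lists dose limiting toxicities as a secondary safety endpoint.
- V.D2 excludes at entry "Hepatic insufficiency with liver function tests (LFTs) > 3 times upper limit of normal" and "Renal insufficiency as defined by creatinine > 1.5 times normal". Subjects below those limits may enroll with values already above normal.
- III.D1 says that the dose-limiting drug-associated toxicity in the animal studies "was hemolysis in rat and significant acute toxicity leading to moribundity". It adds: "All clinical program investigators have been required to monitor hematology parameters".
- VI.B2 schedules chemistry and hematology at Month 1 and Month 3. Month 2 may be a telephone contact. VI.C makes Month 3 the end-of-treatment visit.

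**The concern.** There are two separate weaknesses.

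**No threshold.** The word increased carries no grade, no multiple of ULN and no stated comparison with the subject's own earlier value. A site following the text must call a marginal CPK or ALT exceedance at Month 1 a drug-related DLT and attempt a dose reduction. The endpoint then mixes real toxicity with ordinary laboratory variation, and some subjects may spend the last two months of treatment on less than 500 mg BID for no good reason.

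**The rule does not match its premise.** Four dose-limiting findings go in (liver, muscle, kidney, marrow/hemolysis) and only the first three come out. A trivial chemistry rise is a named DLT, while a hemolytic fall in hemoglobin is not named at all. For a section written to define DLTs clearly, that is a gap in the rule itself. It also instructs sites, so a statistical analysis plan could not repair it.

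**Working it through.** **Step 1. Does another section supply the missing grade or baseline reference?**

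| Section | What it grades or limits | Applies to DLTs? |
|---|---|---|
| X.C5 | AE severity, by CTCAE v4.03 | No |
| VII.D2 | Recording Grade 3 or 4 laboratory abnormalities as AEs | No |
| X.C9 | INR Grade 2 or higher, dose halved | No; INR only, not called a DLT |
| V.D2, items 12 and 13 | LFT and creatinine limits at entry | No; eligibility only |

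None does. X.C9 shows that the protocol ties a dose reduction to a CTCAE grade when it chooses to.

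**Step 2. Compare premise and rule.**

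| Finding in the premise | Parameter in the rule |
|---|---|
| ALT, AST | LFT |
| Rhabdomyolysis | CPK or CK |
| Renal dysfunction | BUN/Cr |
| Marrow toxicity, hemolysis | none named |

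VII.D2 lists bilirubin and LDH under its liver panel, so a broad reading of LFT could pick up hemolysis indirectly. D3 glosses LFTs as ALT and AST in its premise and does not settle the matter. Red cell count, hematocrit and hemoglobin are collected but not used.

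**Step 3. How often would an inert drug trigger the rule?** The protocol states no DLT rate, so there is no figure to reproduce. What follows is an illustration, and every rate in it is assumed.

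- Analytes: ALT, AST, BUN, creatinine, CPK (five).
- Chance p that one value exceeds ULN without drug effect: 1%, 2.5% or 5%. The middle value is the upper tail of a 95% reference range.
- Normal values; between-visit correlation 0.5 or 0.7; between-analyte correlation 0 or 0.4; 400,000 simulated subjects per setting.
- Event: above ULN at Month 1 and not above at baseline, in at least one analyte.
- Expected subjects = 40 × rate, or 60 × rate if all 20 adaptive subjects are added. Chance of at least one in 40 = 1 − (1 − rate)^40.

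| p | New exceedance at Month 1 | Of 40 | Of 60 | At least one in 40 |
|---|---|---|---|---|
| 1% | 3.3–4.3% | 1.3–1.7 | 2.0–2.6 | 74–83% |
| 2.5% | 7.1–9.8% | 2.8–3.9 | 4.2–5.9 | 95–98% |
| 5% | 12.2–17.5% | 4.9–7.0 | 7.3–10.5 | over 99% |

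**Step 4. How far does the answer move with the reading?** These figures use independent tests at p = 2.5%.

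- Five analytes over Month 1 and Month 3, any value above ULN: 1 − 0.975^10 = 22.4%. With equal correlation of 0.3 to 0.5 it is 14 to 18%.
- All seven liver tests plus BUN, creatinine and CPK, two visits: 1 − 0.975^20 = 39.7%; with the same correlations, 21 to 28%.
- Any rise at all over baseline (chance 0.5 per test), five analytes, one visit: 1 − 0.5^5 = 96.9%.

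The text does not choose between these readings, and the counts they give are far apart.

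**The case against.** The strongest reply is that the rule is deliberately sensitive. Monkeys became moribund after two to four doses, with muscle and kidney damage, and III.D1 calls monkey the most sensitive species. A low trigger followed by a call to the medical monitor is precaution, and a Grade 2 threshold would give some of that up. This stands as an argument about which grade to choose. It does not excuse leaving the grade unstated. The presumption that these events are drug-related belongs to the same caution and is not challenged here.

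The choice of analytes also has a rationale. From III.D1, exposure at the rat NOAEL relative to human exposure is 37,717/1,960 = 19 to 56,500/1,890 = 30 for Cmax, and 149,495/11,000 = 14 to 297,000/10,480 = 28 for AUC. The stated monkey margins are 7 to 12 and 4 to 8. Rat hemolysis at 300 mg/kg/day was mild and not considered adverse; it was adverse at 1,000 mg/kg/day. That lowers the urgency, but D3 itself still lists hemolysis among its reasons.

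A reader might infer stronger claims that the document does not support:

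- *A fall in hemoglobin can never be a DLT.* D3 does not say that its list is exclusive, and bilirubin or LDH may count as LFTs. Other routes also exist: III.G maintains the dose only without treatment-emergent toxicity, VI.H item 2 requires stopping for a related AE when continuing is judged detrimental, and X.C2 gives blood dyscrasias as an example of events usually considered serious.
- *An unchanged entry elevation is a DLT.* That strains the word increased, and a value present before the first dose cannot sensibly be attributed to the drug. The wording would be safer if it said so.
- *The primary endpoint is affected.* A DLT label does not make an event serious under X.C2.

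**Conclusion.** The point holds in a limited form. As written, D3 lets minor on-treatment chemistry variation be designated a drug-related DLT with an attempted dose reduction, and it states no hemoglobin criterion for a toxicity that its own premise calls dose-limiting.

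The consequence is modest. No stopping or escalation rule uses the DLT count, and chemistry and hematology are separate safety endpoints. Of the scheduled laboratory visits only Month 1 can change dosing, and the medical monitor is contacted. Hemolysis remains monitored through routine hematology and AE recording.

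The size, 3 to 4 of 40 subjects at Month 1 in the central case, rests on the assumed 2.5% exceedance rate, normality, the chosen correlations and the narrow five-analyte reading. The 95 to 98% chance of at least one false DLT follows from having 40 subjects and should not be read as a measure of harm. This is a cheap improvement; it changes no trial conclusion.

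**What to change.** Amend D3 in two places.

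1. **Chemistry.** Name the analytes that count as LFTs. State that a DLT is a treatment-emergent worsening from the subject's own baseline to a stated CTCAE v4.03 grade. If an analyte has no grade there, give a multiple of ULN. The sponsor's medical team sets the grade: new or worsening Grade 1 keeps the rule sensitive, and Grade 2, as in X.C9, is an option. Smaller rises are still reported to the medical monitor. The presumption of relatedness can stay, and the dose action need not wait for a repeat test.
2. **Hemolysis.** Add a CTCAE v4.03-graded hemoglobin decrease from baseline accompanied by a rise in bilirubin or LDH.

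The cost is amendment wording only. Hemoglobin, bilirubin, LDH, ALT, AST, BUN, creatinine and CPK are already collected at baseline, Month 1 and Month 3, and CTCAE v4.03 is already the grading system. The downside is that some low-grade rises lose the DLT label, though they remain in the laboratory data and still reach the medical monitor.

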Under an adaptive design strategy, additional subjects (up to 20) may be added to increase the number of biomarker responsive idiopathic PD subjects. Given that the investigational drug targets an enzyme key to glutathione synthesis and that glutathione depletion has been found to be associated with PD, we are seeking to determine the safety and potential biochemical benefit of EPI-589 in PD subjects as assessed by glutathione cycle biomarkers. If we determine that there are a subset of idiopathic PD patients—whether due to disease stage or baseline biomarker profile—who are more likely to be EPI-589 responsive, we will seek to enroll additional numbers of these subjects in the adaptive phase so that we can increase the number of likely biomarker responsive subjects. EPI-589 will be administered for up to 3 months (85 days \pm 3 days) unless discontinued for safety or tolerability issues.

A1. Screening Phase

Suitable candidates for the trial will receive a short overview of the study by the Investigator's staff and, if interested, will undergo Screening. The Investigator will inform each prospective subject of the nature and details of the study, explain the potential risks and must obtain written informed consent from the subject or their legally authorized representative prior to performing any study related procedures.

A2. 30-Day Run-in Phase

Once eligibility is confirmed, the subject will be enrolled in the study and the run-in scans, CNS, blood-based biomarker, urine-based biomarker and clinical measurements will be collected.

A3. Baseline

Baseline assessments, scans, blood-based biomarker, urine biomarker, and clinical measurements will be collected.

A4. Treatment Phase

EPI-589 dosing will start on Day 1. Subjects will self-administer EPI-589 at a dose of 500-mg BID (morning and evening dose along with food).

Blood-based biomarker, urine biomarker, and clinical measurements will be collected at Day 29 (\pm 3 days) and Day 85 (\pm 3 days).

A5. End of Treatment

End of treatment data will be collected at the last study visit Day 85 (\pm 3 days).

AEs reported as ongoing at Day 85 (\pm 3 days) and/or any concomitant medications associated with such events will be followed for up to 30 days, until the event resolves, or until the Sponsor and the Investigator agree that further follow-up is not medically necessary.

A6. Post-Treatment Follow-up

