9. MDS-UPDRS
10. MoCA
11. DaTscan (for idiopathic subjects only)
12. Revised Hamilton Rating Scale for Depression
13. SAE assessments
14. Concomitant medications assessment (last 60 days prior to enrollment)

*Breast exam is at screening physical exam only.

** Height is measured at screening visit only.

***Screening values can be used if done within one month of baseline and if completed under fasted conditions

A1. Run-in Assessments

If the subject is eligible for the study following all screening procedures and is still willing to participate in the study, the subject must return to the clinic within one month for Run-in assessments. These will be performed 30 days (\pm 3 days) prior to baseline after eligibility is confirmed and subject is enrolled in the study. Run-in evaluations consist of the following:

1. Fasting blood-based glutathione cycle biomarkers
2. Fasting CNS biomarkers (lumbar puncture)
3. Fasting urine biomarkers
4. Timed motor tests (for subjects on dopamine therapy)
5. AE/SAE assessments
6. Concomitant medications review

B. Treatment Phase

After the Run-in phase, the subject must return to the clinic within 30 days (± 3 days) for baseline assessments. In-clinic study visits are scheduled at Month 1 and Month 3. The Month 2 study assessments can be conducted via telephone. End of treatment assessments will be conducted at the Month 3 study visit. Pharmacokinetic sampling takes place at Month 1 and Month 3. The baseline and all subsequent laboratory assessments should be obtained under fasting conditions.

B1. Baseline Assessments

The following will be assessed or performed at this visit.

1. Physical examination including vital signs
2. Height and weight*
3. 12-Lead ECG*
4. Fasting blood-based GSH cycle biomarkers
5. Fasting urine-based biomarkers
6. Laboratory assessments for hematology, coagulation and serum chemistry*
7. Urine pregnancy test (females of child bearing potential)
8. C-SSRS (Columbia Suicide Severity Rating Scale)

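### Section VIII.A gives no place to the untreated run-in change already collected, and adaptive enrolment by biomarker profile has no biomarker sample before enrolment

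*Protocol*

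**What the plan says.** Section VIII.A calls the study subject-controlled and open-label, and gives one efficacy contrast: "changes from baseline to Month 3 for disease-relevant peripheral and CNS biomarkers as well as clinical measures will be calculated for each subject". Section VII.F1 says that blood, urine and CNS glutathione levels "will be used to evaluate EPI-589 target engagement and ability to correct a key biochemical aspect of disease pathology". There is no reference arm.

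The visit lists in Section VI.A to VI.B2 fix when each measure is taken:

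| Measure | Screening | Run-in | Day 0 | Month 1 | Month 3 |
|---|---|---|---|---|---|
| Blood and urine glutathione markers | no | yes | yes | yes | yes |
| Timed motor tests (subjects on dopamine therapy) | no | yes | yes | no | yes |
| CSF | no | yes | no | no | yes |
| MDS-UPDRS | yes | no | yes | yes | yes |
| MoCA | yes | no | no | no | yes |

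The run-in list in VI.A1 includes both "Fasting blood-based glutathione cycle biomarkers" and "Fasting CNS biomarkers (lumbar puncture". The first dose follows the Day 0 assessments.

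Section V.A allows up to 20 more idiopathic subjects if a more responsive subset is found, "whether due to disease stage or baseline biomarker profile". In that case "we will seek to enroll additional numbers of these subjects in the adaptive phase". Sections V.C2 and VIII.D place these subjects under the same protocol. On the order of events, V.A2 says: "Once eligibility is confirmed, the subject will be enrolled in the study and the run-in scans, CNS, blood-based biomarker". VI.A1 times the run-in visit "prior to baseline after eligibility is confirmed and subject is enrolled in the study".

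**The concern.** There are two separate points.

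First, a change from Day 0 to Month 3 in one treated group combines any drug effect with drift over time and visit-to-visit noise. Without a second arm, the only view of drift and noise in these subjects is the interval before dosing. The schedule already measures blood, urine and timed motor tests at both ends of that interval, but the stated analysis does not report the result. A shift in glutathione could then be read as target engagement with nothing untreated beside it.

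Second, choosing adaptive-phase subjects by biomarker profile needs a biomarker value before the choice is made. The visit order supplies the first value only after the subject is enrolled, at the visit where the lumbar puncture is done. A candidate whose profile turns out not to fit would already be enrolled and might already have had the puncture. The withdrawal reasons in VI.H contain no entry for such a subject.

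**Working it through.** The protocol gives subject numbers but no precision, power or effect size (VIII.D), so there is no stated figure to reproduce.

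**Step 1. Intervals.** Run-in is 30 ± 3 days before Day 0 (VI.A1), which gives 27 to 33 untreated days. Month 3 is Day 85 ± 3 (VI.B2), which gives 82 to 88 days from Day 0.
- CSF, run-in to Month 3: 27 + 82 = 109 to 33 + 88 = 121 days.
- Untreated share of the CSF interval: 27/(27 + 88) = 23.5% to 33/(33 + 82) = 28.7%.
- A linear drift would be larger in CSF than in blood or urine by 115/88 = 1.31 to 115/82 = 1.40 times.

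**Step 2. Precision of the untreated change.** Assume equal, independent visit error with within-subject SD *s*. A change between two visits then has variance 2*s*², and the 95% CI half-width for its mean is t(0.975, n−1) × √(2/n), in units of *s*.
- n=40: 2.023 × 0.2236 = 0.45
- n=20: 2.093 × 0.3162 = 0.66
- n=10: 2.262 × 0.4472 = 1.01

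Under the same assumption the Day 0 to Month 3 change is equally precise, so a step shift between visits shows equally well in either. For linear drift, the 30-day change must be scaled to 85 days:
- n=40: 0.452 × 85/30 = 1.28 (0.452 × 82/33 = 1.12 to 0.452 × 88/27 = 1.47 over the windows)
- n=20: 0.662 × 85/30 = 1.88

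**Step 3. Why not subtract.** The standard error of a contrast is proportional to the root of the sum of its squared coefficients.
- Day 0 to Month 3: 1 + 1 = 2.
- Treated change minus untreated change, coefficients (1, −2, 1): 6. The ratio is √(6/2) = 1.73.
- With the untreated change scaled by 85/30: 2.833² + 3.833² + 1 = 23.72. The ratio is √(23.72/2) = 3.44.

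Subtraction would therefore cost much precision. Showing the two changes side by side costs none.

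**Step 4. Order of enrolment and sampling.** The screening list in VI.A has no glutathione sample. V.A2 and VI.A1 both put enrolment before the run-in draw. Disease stage is different: MDS-UPDRS is done at screening, and its Part III includes the Hoehn and Yahr scale (VII.F2.a).

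**Step 5. Why the selecting sample should not be the baseline.** This is an illustration only; the cut-off, direction and ICC are assumptions. If the lowest fraction *q* were selected and change were measured from that same sample, a drug with no effect would show (1 − ICC) × φ(z_q)/q total SDs.
- q=1/3: 1.09 × 0.2 = 0.22 (ICC 0.8) and 1.09 × 0.5 = 0.55 (ICC 0.5).
- q=1/2: 0.798 × 0.2 = 0.16 and 0.798 × 0.5 = 0.40.

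With independent visit errors, selecting on the run-in value leaves Day 0 to Month 3 at an expected zero, because both later values have regressed equally. The same 0.16 to 0.55 SD then falls on the run-in to Day 0 change. Selecting on a separate screening sample leaves all later changes at zero.

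**The case against.** The choice of summaries is commonly left to a statistical analysis plan, and VIII.A does not say that its contrast is the only one. This stands in part: a reader might infer that the run-in data will never be used, but that is shown only for the text of VIII.A.

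A reader might also infer that the baseline to Month 3 change is undefined or wrong for CSF and MoCA, since neither is measured at Day 0. The documents do not support this. The synopsis and Section V.A describe the run-in as the period that sets the biomarker and clinical baseline, and V.A3 leaves CNS markers out of the Day 0 visit. CSF has one pre-dose value (run-in) and MoCA has one (screening), and each can serve as baseline. What remains for CSF is a matter of labelling.

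The untreated check is weak. At about ±1.3 within-subject SD when scaled, it would rarely settle a question of drift, and timed motor tests have fewer subjects still. This stands, and it is why the check should be shown as coarse and not subtracted.

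The adaptive point is conditional. The phase is optional, and disease stage is an alternative criterion that is available at screening. A reader might infer that the whole adaptive phase is unworkable, but only the biomarker-profile route is. A reader might also take the 0.16 to 0.55 SD as a bias in this trial. It is not one: the protocol states no cut-off, direction or ICC, and selecting on run-in would leave the Day 0 to Month 3 change unbiased.

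**Conclusion.** The point holds in two limited parts and should be corrected. VIII.A reports only the baseline to Month 3 change, although an untreated change over 27 to 33 days exists for blood, urine and timed motor tests. Reporting it is a free gain in a single-arm study. Its value is modest: half-width 0.45 within-subject SD at n=40, or about 1.3 scaled to 85 days, assuming equal and independent visit error and both values present in every subject.

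Enrolment by baseline biomarker profile cannot work in the stated visit order. That is a design fact which no analysis plan can repair. It affects one optional route.

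CSF and MoCA baselines are not errors. CSF change does cover 109 to 121 days, of which 23-29% are untreated, and has no untreated comparison, so it should not be read as matching the blood and urine changes. The biomarkers are secondary, and the primary safety endpoint is unaffected.

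**What to change.** 1. **Section VIII.A.** For blood, urine and timed motor tests, report the run-in to Day 0 change beside the Day 0 to Month 3 change. Give each a 95% CI and its interval length, do not subtract one from the other, and describe the untreated change as a coarse check. State that CSF change runs from run-in, includes untreated days and has no untreated comparison. If a screening to Day 0 change in MDS-UPDRS is shown, note that the screening value is tied to the Hoehn and Yahr eligibility limit. This costs only wording and tabulation of data already collected.

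2. **Section V.A.** If adaptive subjects are chosen by biomarker profile, make the choice before enrolment and lumbar puncture. Use a fasting blood or urine sample at screening that does not also serve as the value from which change is measured. Tabulate these subjects separately from the first 20 idiopathic subjects. This costs one extra fasting screening sample, and only if this route is used. If it is blood, it counts toward the limit of less than 100 mL in Section VII.D2.
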